8.1.2 Procedure Supplies Provided by the Sponsor

1. Bashir™ Endovascular Catheter

8.2 Baseline Hemodynamic Readings

The following readings will take place using the Swan-Ganz or angled pigtail catheter in the IR suite/Cath lab prior to placement of the Bashir™ Endovascular Catheter(s). Print out the initial baseline readings for the PA pressures and retain with the source documentation in the subject binder. Indicate where on the tracing the PAS, PAD and PA Mean are interpreted.

1. PA Pressures measured using a Swan-Ganz catheter or angled pigtail: PAS / PAD / PA Mean
2. SpO₂ – Arterial Oxygen Saturation (pulse oximeter O₂ saturation)
3. SvO₂ - Mixed Venous Oxygen Saturations (from tip of a pigtail catheter or Swan-Ganz Catheter PA port)
4. CO – Modified Fick Calculation (see terms and definitions for formula)
5. CI – Calculation

9.0 BASHIR™ ENDOVASCULAR CATHETER INVESTIGATIONAL PROCEDURE

Please refer to the Instructions for Use for complete instructions on preparation, use, and handling of the Bashir™ Endovascular Catheter (BEC).

9.1 Baseline Readings - Summary of Procedure Steps

1. It is recommended that the patient's blood pressure is under control prior to the investigational procedure, with BP < 180/110 mmHg prior to PMCDT.
2. Discontinue the peripheral IV heparin drip infusions.
3. Obtain venous access using ultrasound guidance and Micropuncture needle. Ultrasound guidance and use of Micropuncture needle is mandatory for both CFV and IJ access.
4. Place 7F sheath(s) or larger in the RCFV or access point of choice (LCFV or IJ).
5. Check ACT - If ACT < 200 seconds, administer additional heparin bolus until ACT is documented to be \geq 200 seconds.
6. Using a .035in. exchange length wire, insert the wire into a sheath and advance it up to the right atrium.

7. Insert the Swan-Ganz or angled pigtail catheter over the wire and advance it up to the right atrium.
8. Remove the guide wire.
9. Float the Swan-Ganz catheter or angled pigtail, and record baseline hemodynamic data in section 8.2.
10. Insert the exchange length STORQ™ (Cordis) guide wire, or equivalent, into the Swan-Ganz or angled pigtail catheter. Remove the Swan-Ganz or angled pigtail catheter.
11. Exchange the Swan-Ganz Catheter, or angled pigtail, for a long 7F sheath (or larger) which is placed into the PA where the thrombus is located.
12. Remove the guidewire and the dilator carefully from the PA making sure that the sheath does not jump forward.

9.2 Bashir Endovascular Catheter Use – Procedure Steps

1. Prepare all r-tPA solutions and IV infusion mixtures in Section 9.3 prior to opening the Bashir Endovascular Catheter (BEC).
2. Prepare the BEC for use:
 - a. Ensure that the infusion basket of the BEC can be expanded and collapsed by moving the actuator on the handle backward and forward while depressing the white button.
 - b. With the basket expanded, flush the basket infusion port with standard flush solution. Observe for flush solution exiting the infusion holes of the basket. Collapse the basket.
 - c. Flush the wire lumen of the BEC observing that flush solution exits the tip of the catheter.
3. Using a .018in x 300cm length steel core guide wire, such as Hi-torque Steelcore Peripheral Guide Wire (Abbott Vascular), introduce the wire into the lumen of the long sheath(s) and advance up into the target pulmonary artery.
4. Backload the BEC onto the 0.018" guidewire and advance towards the long sheath. DO NOT insert the BEC into the sheath.
5. Attach a three-way stopcock to the infusion basket port of the BEC.
6. Commence r-tPA infusion via the stopcock on the basket infusion port using an infusion pump. Start the infusion through the BEC PRIOR TO inserting the catheter into the sheath. This is to maintain patency during catheter insertion, advancement, and positioning in the patient.
7. Advance the BEC into the target PA.
8. Do NOT aspirate back from the basket infusion port to back bleed. Only maintain forward flow by infusing the r-tPA at the prescribed rate 95cc/hour for unilateral PE and 65cc/hour for bilateral PE, as stated in Table 2.
9. Keeping the wire in the central wire lumen expand the infusion basket of the BEC.

9.3 r-tPA Administration

9.3.1 Part 1 – r-tPA Pulse Spray - In the IR suite/Cath lab through the BEC

1. Reconstitution of r-tPA Pulse Spray Mixture

- a. Obtain a 2.2mg vial of r-tPA (1mg/ml) provided by study site.

- b. Mix the lyophilized powdered r-tPA with 2.2ml sterile water for injection provided by study site (as stated in the r-tPA information sheet) to obtain 1mg/ml. Do not use bacteriostatic sterile water for injection.
- c. Aspirate exactly 1mg (1ml) into a 3cc syringe (for accuracy)
- d. Inject 1mg (1ml) of r-tPA mixture into a 10cc syringe, and aspirate 0.9% NaCl to have a maximum of 10cc of diluent and drug mixture in the syringe.
- e. Repeat (c) and (d) above x 1.
- f. This equals two (2) 10cc pulse spray doses (1mg/10cc in one 10cc syringes per pulse spray) with 1mg r-tPA per dose -Total of 2 mgs of r-tPA for unilateral PE).
- g. If treating bilateral PE, repeat steps (c) through (f) above.

Table 2. r-tPA Doses and Mixtures for Pulse Sprays and Infusions through the BEC Provided by Site

Pulse Sprays						Infusion		
	No. of 2mg Cathflo r-tPA Vials Required	Diluent: Sterile Water for Injection	Total Diluent Required 0.9% NaCl	Total Dose per Syringe	Total Syringes for Pulse Sprays	Number of 2mg Cathflo™ r-tPA Vials Required	Amount of Diluent Required 0.9% NaCl	Infusion Rate
Unilateral PE	1	2.2 ml per vial to have 1mg/ml	Total of 20cc including r-tPA	2 mg in 20 cc divided into 2 10cc syringes	2 pulse sprays in two 10cc syringes = two 10cc syringes	5 (10mg x 1 infusion)	750cc total including r-tPA mixture x 1 bag	95cc/hr= 1.27mg/hr x 1 infusion until complete 10mg total
Bilateral PE	2	4.4 ml in 2 vials for 1mg/ml	Total of 40cc including r-tPA	2 mg in 20cc x 2, divided into four 10cc syringes	2 pulse sprays in two 10cc syringes = four 10cc syringes	5 (5mg x 2 infusions)	500cc total including r-tPA mixture x 2 bags	65cc/hr= .65mg/hr per infusion x 2 infusions until complete 10mg total

2. Reconstitution of r-tPA IV Infusion Mixture

- a. Unilateral PE
 - i. Obtain a 1,000cc bag of 0.9% NaCl for infusion.
 - ii. Aspirate 250cc of 0.9% NaCl from the 1,000cc IV bag to have a total diluent of 750cc.
 - iii. Mix five (5) vials (2.2 ml injected into 2.2 mg vials) of r-tPA with sterile water for injection until the lyophilized powder is dissolved, for a total of 10 mg of r-tPA.
 - iv. Aspirate 10ml (10mg) into a syringe.
 - v. Verify 10ml are aspirated in the syringe.

- vi. With a new syringe aspirate the amount of fluid from the IV bag that is equal in amount to the r-tPA solution in the r-tPA syringe, 10ml, so the total volume in the bag with the r-tPA will be 750cc.
- vii. Inject the 10 mg solution of r-tPA into the IV bag for infusion. You should have a total of 10mg of r-tPA in a total of 750cc of diluent.
- viii. Set aside for use at the end of the pulse spray procedure(s).

- b. Bilateral PE
 - i. Obtain two (2) 500cc bags of 0.9% NaCl for infusion.
 - ii. Mix five (5) vials of r-tPA with sterile water for injection until the lyophilized powder is dissolved, for a total of 10mg of r-tPA (1mg/ml).
 - iii. Aspirate 10ml (10mg) dose into a syringe.
 - iv. Verify 10ml are aspirated into the syringe.
 - v. Determine the total number of mls in the syringe and note 5ml is one-half of the volume of the solution for one-half of the dose.
 - vi. With a new syringe aspirate the amount of fluid from the IV bag that is equal in amount to one-half of the r-tPA solution in the r-tPA syringe, 5ml, so the total volume in the bag with the r-tPA will be 500cc once the 5mg of r-tPA is added to the IV bag. Repeat for second IV bag.
 - vii. Inject 5mg (5ml) solution of r-tPA into one (1) IV bag for infusion. Inject the second 5mg solution of r-tPA into the second IV bag for infusion. You should have a total of 5mg of r-tPA in a total of 500cc of diluent in each IV bag for bilateral PE, a total of 10mg split among the two IV bags.
 - viii. Set aside for use at the end of the pulse spray procedure(s).

3. Pulse Spray of r-tPA for Unilateral and Bilateral PE

- a. **Unilateral PE:** With the catheter in the target PA, and after verification the basket portion of the catheter has exited the sheath under fluoroscopy, and guidewire in place, expand the basket of the catheter to the desired diameter making sure that the infusion limbs are expanded to less than the diameter of the vessel wall.
- b. Attach the pulse spray syringe to the unused port of the stopcock attached to the basket infusion port. Pause the infusion pump of the r-tPA infusion. Turn the stopcock so that it is closed to the infusion pump line and open to the syringe and to the basket infusion port.
- c. Administer 10cc (1mg r-tPA in 10ml) of pulse spray, from the 1st syringe of two syringes, into the thrombus at a steady rate over 10-15 seconds.
- d. Under fluoroscopy, and guidewire in place, collapse the basket and re-expand the basket.
- e. Repeat this with the second 10cc syringe (1mg r-tPA in 10ml) over 10-15 seconds.

- f. As soon as the pulse sprays are administered, immediately re-start the r-tPA infusion via the basket infusion port of the BEC.
- g. **Bilateral PE:** Repeat steps a-f in contralateral pulmonary artery for bilateral PE.
- h. Once pulse sprays are complete, the basket(s) should remain expanded.
- i. As soon as the pulse sprays are administered, immediately re-start the r-tPA infusion via the basket infusion port of the BEC in accordance with Table 2. Refer to Section 9.3.2 and Table 2 for r-tPA infusion instructions.
- j. Remove the guidewire(s) from the wire lumen(s).
- k. Ensure the BEC(s) are adequately flushed. Attach the flushed pressure transducer tubing to the wire lumen of the BEC(s). Measure the systolic PA, diastolic PA, and mean PA pressures in each PA with a pulmonary embolism from the tip of the BEC through the guidewire lumen at the back of the BEC handle. Print the PA waveform tracings and mark the tracings where the systolic PA, diastolic PA, and mean PA pressures are interpreted and documented.
- l. If the waveform is damped, adequately flush the wire lumen. If the waveform is still damped after it is flushed, print the damped waveform on paper, and retain the waveform with the source documentation for this study. Measure the systolic PA, diastolic PA, and mean PA pressures in each PA with a pulmonary embolism on the tracing. If the waveform becomes phasic prior to leaving the lab, print the waveform, mark on the waveform where the systolic PA, diastolic PA, and mean PA pressures are interpreted and the time the waveform became phasic. Retain the printout with the source documentation for this study.

9.3.2 Part 2 – r-tPA Infusion and Anticoagulation – Prior to Departing the IR suite/Cath lab r-tPA Infusion

Upon completion of the Pulse Sprays, with the basket re-expanded and catheter securely in place, begin r-tPA solution infusion(s), as soon as possible (immediately following the pulse sprays).

1. **For unilateral PE:** The total r-tPA is 10mg at 1.27mg/hr. Using an IV pump at 95cc/hour, infuse the 750cc of 0.9% NaCl with the 10mg r-tPA at 1.27mg/hr until infusion is complete (approximately 8 hours).
2. **For bilateral PE:** The total r-tPA dose is 10mg at 1.30mg/hr. Using two (2) IV pumps at 65cc/hour, infuse the 500cc of 0.9% NaCl x 2 simultaneously with the 5mg r-tPA at 0.65mg/hr for each PE for a total of 1.3mg/hour until complete (approximately 8 hours).
3. **Anticoagulation:** Re-start low dose heparin infusion into each sheath to prolong the aPTT (suggested range 40 to 60 seconds) prior to leaving the

IR suite/Cath lab to maintain therapeutic dose through completion of the 48-hour CT scan.

The institution is to follow the standard of care for the administration of heparin and the monitoring of aPTT in addition to the aPTTs measured at certain time points required by this protocol.

4. **Maintaining Patency Through the Central Lumen of the BEC(s):**
Remove the wire from the central lumen of the BEC and attach a 3-way stopcock and flush with heparinized saline to maintain patency in the central lumen of the BEC (both BECs if bilateral PEs) when transferring to ICU.

If it is standard of care in the IR suite/Cath lab to attach pressure tubing prior to transfer to the ICU for continuous PA pressure monitoring in the ICU, that may be done in lieu of heparinized flush in a syringe to maintain patency when transferring from the IR suite/Cath lab to the ICU. The central lumen of the BEC will be used for continuous monitoring of the PA pressures in the ICU. Hospital standard protocol will be used to maintain patency of the central lumen and to perform continuous pressure monitoring through the BEC in the ICU.

For example, heparinized saline to a pressure bag and pressure monitor tubing connected to the bedside monitor to transduce pressure from the central lumen of the BEC may be performed; if there are two BECs in place for bilateral PEs, the central lumen of both BECs require pressure tubing for continuous pressure monitoring and kept open with standard pressure tubing transduced to the bedside monitor using heparinized saline in a pressure bag to keep the line patent and for continuous PA pressure monitoring and SvO_2 draws.

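### Section 9.3.1 sets the mixed r-tPA infusion bags aside until the pulse sprays are over, but section 9.2 step 6 needs that infusion started before the catheter enters the sheath

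*Combined protocol and SAP*

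**What the plan says.** Section 9.2 step 1 directs staff to the mixing instructions first: "Prepare all r-tPA solutions and IV infusion mixtures in Section 9.3 prior to opening the Bashir Endovascular Catheter (BEC". Those instructions are in section 9.3.1 item 2, for unilateral PE (2a) and bilateral PE (2b). Both lists finish with the same line: "Set aside for use at the end of the pulse spray procedure(s".

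The handling steps in section 9.2 give a different order. Step 2b has staff "flush the basket infusion port with standard flush solution". Step 4 loads the catheter (BEC) on the guidewire but forbids inserting it into the sheath, and step 5 attaches the stopcock. Step 6 then says "Start the infusion through the BEC PRIOR TO inserting the catheter into the sheath" and explains that this keeps the catheter patent while it is inserted, advanced and positioned. Step 7 advances it into the target artery. Step 8 adds "Only maintain forward flow by infusing the r-tPA at the prescribed rate", with the Table 2 rates.

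The pulse-spray steps in section 9.3.1 item 3 follow the section 9.2 order. Item 3b says "Pause the infusion pump of the r-tPA infusion", and items 3f and 3i say "immediately re-start the r-tPA infusion via the basket infusion port of the BEC".

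Two other places use the order of the mixing lines. Section 9.3.2 tells staff, after the sprays, to "begin r-tPA solution infusion(s), as soon as possible (immediately following the pulse sprays". The supply list in section 8.1.1 item 13 (i and ii) has the infusion starting once the procedure ends.

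**The concern.** The two orders cannot both be followed. Pulse sprays are given only after the catheter is in the target artery (section 9.3.1 item 3a). A bag held back until they are finished therefore cannot have been running before the catheter entered the sheath.

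Because section 9.2 step 1 sends staff through the mixing lines before the BEC is opened, the instruction to hold the bag is read before the instruction to start it. If it were obeyed, no r-tPA would pass through the basket port from section 9.2 step 7, when the catheter is advanced, until the first pulse spray at section 9.3.1 item 3c. Step 6 exists to prevent that gap. The version table in section 19.0 gives the reason for the early start: to stop blood clotting in the infusion limbs of the basket. The table is cited for that reason only; the contradiction lies between lines of the current text.

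**Working it through.** The plan states no figure for this point. The check has three parts.

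**1. Is it the same bag?** Inputs are from Table 2 and section 9.2 step 8. Unilateral: 10 mg in 750 cc at 95 cc/hr. Bilateral: 5 mg in 500 cc at 65 cc/hr through each of two catheters. Formulas: mg/hr = rate × dose / volume; hours = volume / rate.

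- Unilateral: 95 × 10 / 750 = 1.267 mg/hr (plan: 1.27); 750 / 95 = 7.89 h (plan: about 8).
- Bilateral, per catheter: 65 × 5 / 500 = 0.65 mg/hr (plan: 0.65); 500 / 65 = 7.69 h (plan: about 8).

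The step 8 rates reproduce the Table 2 doses, and no separate priming bag is described. The bag to be set aside is the one that step 6 starts.

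**2. Which order is intended?**

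| Place | When the infusion first runs |
|---|---|
| 9.2 step 6 | before the catheter enters the sheath |
| 9.2 step 8 | already running, at the Table 2 rate, after advancement |
| 9.3.1 item 3b | already running; paused for the spray |
| 9.3.1 items 3f, 3i | re-started after the spray |
| 9.3.1 items 2a viii, 2b viii | held until the sprays end |
| 9.3.2 | begun after the sprays |
| 8.1.1 items 13 i, 13 ii | started when the procedure ends |

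Five instructions assume an early start, and a pump cannot be paused or re-started unless it has been running. Five places carry the later order: 2a viii, 2b viii, 9.3.2, 13 i and 13 ii. The reference in section 4.3 to an infusion following the sprays is background rationale and is not counted.

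**3. What changes if the wrong line is followed?** The bag runs until complete in either order, so the nominal total is the same:

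- Unilateral: 2 + 10 = 12 mg.
- Bilateral: 2 × 2 + 2 × 5 = 14 mg.

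The documents do not give the time from step 6 to the first spray. Purely as an assumption, take 5 to 30 minutes:

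- Unilateral: 1.267 × 5/60 = 0.11 mg to 1.267 × 30/60 = 0.63 mg.
- Bilateral, per catheter: 0.65 × 5/60 = 0.05 mg to 0.65 × 30/60 = 0.33 mg.

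These amounts come out of the same 10 mg. What differs is the timing and whether there is forward flow during insertion.

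**The case against.** The best defence is that the disputed lines sit in a mixing recipe, while the operator's sequence in section 9.2 is explicit. To insert the catheter without flow, staff would have to pass over step 4's prohibition on insertion, step 5's stopcock, and step 6, which puts the timing in capitals and gives the reason. Item 3b would then show that the pump was not running, although by that time the catheter is in place. The port has been flushed at step 2b, and section 9.1 step 5 requires heparin until the ACT is at least 200 seconds before the BEC steps begin. Item 3i already says to re-start and refers on to section 9.3.2, so the wording there is unlikely to mislead. Section 9.0 also refers users to the Instructions for Use, which are not among the documents. All of this stands and keeps the practical risk small. None of it reconciles the lines.

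Stronger readings are tempting, but the documents do not support them:

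- **That step 8 also requires flow before sheath entry.** It follows advancement at step 7. It supplies the rate and identifies the bag; only step 6 sets the before-sheath requirement.
- **That the bag might not be ready.** Step 1 has every mixture prepared before the BEC is opened. A bag set aside is mixed; at most it is not connected.
- **That the dose or the endpoints are compromised.** The nominal dose is 12 or 14 mg in either order, and a shift in start time within the procedure does not materially affect the 72-hour bleeding endpoint or the imaging endpoints.
- **That device success becomes unattainable, because section 6.2.1 defines it as use of the BEC according to the protocol.** The intended order is recoverable from section 9.2 and section 9.3.1 item 3, and nothing in the plan makes this mixing line a criterion of success.

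**Conclusion.** The point holds as a minor internal inconsistency that is wrong as written. Section 9.3.1 items 2a viii and 2b viii cannot be obeyed together with section 9.2 step 6, and section 9.3.2 and section 8.1.1 items 13 i and ii conflict with step 6 in the same way. The early start is itself a deliberate choice and is not disputed.

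The consequence is limited to a bag that is not connected and a catheter advanced without forward flow. The clotting risk cannot be sized, because the documents give neither the interval nor a patency rate. Confidence is high that the wording conflicts; no clinical effect is claimed. The conclusion assumes that Table 2 lists every infusion preparation. Whether the Instructions for Use repeat the correct order cannot be seen.

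**What to change.** Change the wording in five places:

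1. Section 9.3.1 items 2a viii and 2b viii: replace the line with *Connect to the infusion pump(s) for use at 9.2 step 6; pause during the pulse sprays and re-start afterwards (9.3.1 items 3b, 3f).*
2. Section 9.3.2: change *begin* to *re-start*.
3. Section 8.1.1 items 13 i and 13 ii: give the start as *to be started in the IR suite/Cath lab before BEC insertion (9.2 step 6)*.

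Each edit repeats what section 9.2 step 6 and section 9.3.1 item 3 already require. The cost is text only: no new CRF field, test, visit or patient.

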7.0 METHODOLOGY

7.1 Pre-Procedure Testing Within 48 Hours Pre-Procedure

7.1.1 Laboratory Tests

1. **CMP, CBC, Cardiac Biomarkers Troponin I and BNP** – These tests will be drawn within 48 hours pre-procedure.
2. **aPTT** – Drawn within 48 hours pre-procedure. Unfractionated heparin will be infused to prolong the aPTT (suggested range is 60-80 seconds) prior to the administration of r-tPA. The institution is to follow the standard of care for the administration of heparin through the completion of the r-tPA infusion and the monitoring of aPTT in addition to the aPTTs measured at certain time points required by this protocol.
3. **International Normalized Ratio (INR)** – INR will be drawn within 48 hours pre-procedure for patients who are on Coumadin and must be ≤ 1.5 to be eligible for enrollment. Patients who are on Coumadin and have an INR ≤ 1.5 who are in the study the coumadin will be discontinued during the heparin infusion and the r-tPA infusion and can be restarted prior to discharge.
4. **Fibrinogen** – Fibrinogen levels are required to be checked within 48 hours prior to the procedure. *The assay method must be recorded (e.g. Clauss, PT-derived fibrinogen assay, immunological, gravimetric, other)*

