7.1.4 Anticoagulation

Unfractionated heparin is required to be used for anticoagulation and is to be started pre-procedure by intravenous administration to prolong the aPTT (suggested range is 60-80 seconds) unless the patient has received Lovenox.

The institution is to follow the standard of care for the administration of heparin and the monitoring of aPTT in addition to the aPTTs measured at certain time points required by this protocol. Stop the heparin administration at the completion of the r-tPA infusion. The final aPTT should be measured according to standard of care.

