7.1.5 Patients Receiving Lovenox for Treatment of Pulmonary Embolism

Lovenox: Use of Lovenox is permitted pre-procedure for the treatment of PE if it is the standard of care. If Lovenox is administered to a potential study subject, then catheter directed thrombolysis procedure is to start no sooner than 12 hours from the last Lovenox dose.

During the CDT procedure in the IR suite/Cath lab ACTs will be checked and heparin bolus given to achieve ACT ≥ 200 seconds.

After completion of the CDT procedure, a heparin drip will be started prior to leaving the IR suite/Cath lab to maintain therapeutic dose through completion of the r-tPA infusion.

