clot dissolves in each PA with a pulmonary embolism will be known. Please note that printouts are not required for every reading, only when the damped waveform becomes phasic, if damped when subject arrives in the ICU. These readings are required through the completion of r-tPA infusion:

- a. PAS / PAD / PA Mean Pressures
- b. SpO₂ – Arterial Oxygen Saturation (pulse oximeter O₂ saturation)

4. **Mixed Venous Oxygen Saturation (SvO₂):** Record every two (2) hours (± 30 minutes) in the ICU starting after the initiation of the r-tPA infusion. These readings are required through the completion of r-tPA infusion:
 - a. SvO₂ – Mixed Venous Oxygen Saturations (Sample is from tip of the BEC, drawn from the central lumen of the BEC at the end of the handle. If bilateral, either BEC is acceptable for drawing the SvO₂.)
5. **Anticoagulation – Intensive Care Unit During r-tPA Infusion:** Heparin drip should be administered until the r-tPA infusion is complete (approximately 8 hours).
6. **Anti-coagulation Immediately Post-rtPA Infusion:** Once the r-tPA infusion is complete, turn off the heparin gtt. Starting 45 minutes (± 15 minutes) after the r-tPA completion, administer Lovenox 1mg/kg sub-Q every 12 hours (± 30 minutes) through the completion of the 48-hour CTA.
7. **Physical Exam:** A physical exam is required to be performed at the completion of the r-tPA infusion.
8. **Stopping r-tPA Infusion in ICU at the End of 8 Hours:** Upon completion of r-tPA infusion, maintain patency through the BEC by replacing r-tPA with heparinized saline using the infusion pump, at TKO, and transport to IR suite/Cath lab to remove BEC. Heparinized saline should infuse via infusion pump through the basket infusion port until subject arrives at the IR suite/Cath lab for catheter removal.

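### Section 9.3.2 item 3 continues sheath heparin to the 48-hour CT scan, while five other places in the protocol end it when the r-tPA infusion ends

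*Combined protocol and SAP*

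**What the plan says.** Section 9.3.2 covers what is done before the patient leaves the cath lab. Its item 3 reads "Re-start low dose heparin infusion into each sheath to prolong the aPTT (suggested range 40 to 60 seconds") and sets the duration as "IR suite/Cath lab to maintain therapeutic dose through completion of the 48-hour CT scan".

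Five other current places give an earlier end point:

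- 7.1.1 item 2: "The institution is to follow the standard of care for the administration of heparin through the completion of the r-tPA infusion".
- 7.1.4: "Stop the heparin administration at the completion of the r-tPA infusion".
- 7.1.5, for patients given Lovenox before the procedure: "a heparin drip will be started prior to leaving the IR suite/Cath lab to maintain therapeutic dose through completion of the r-tPA infusion".
- 10.1 items 5 and 6, for the ICU: "Heparin drip should be administered until the r-tPA infusion is complete (approximately 8 hours"), and then "Once the r-tPA infusion is complete, turn off the heparin gtt".
- Appendix 21.1 footnote 3: heparin runs until the r-tPA infusion is complete.

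The synopsis lists sheath heparin only under the r-tPA infusion phase and Lovenox under the phase after it. The synopsis, 10.1 item 6 and Appendix 21.1 footnote 3 start Lovenox 1 mg/kg every 12 hours at 45 ± 15 minutes after r-tPA ends. The synopsis, 10.1 item 6, 10.4.1, 10.5.1 and 10.5.2 carry it through the 48-hour CTA.

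**The concern.** Item 3 is a treatment order, written for the staff who start the drip. A site that follows it to the letter leaves heparin running when the ICU gives full-dose Lovenox, hours after a thrombolytic. The primary safety endpoint (6.2.1) is ISTH major bleeding within 72 hours of the start of r-tPA, so the possible harm falls on the outcome the study is meant to describe.

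With up to ten subjects, one major bleed is 1/10 = 10%, the same as the major bleeding rate that section 4.3 cites for SEATTLE II. A bleed under doubled anticoagulation could not be cleanly attributed to the catheter and r-tPA regimen.

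There is also a compliance problem. A site that obeys either instruction departs from the other, although 14.1 item 12 does not permit deviations except to protect the patient.

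**Working it through.** No sample size, power or alpha figure depends on this point, and the plan states no overlap figure to reproduce. The check is a comparison of texts followed by a timing calculation.

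**Step 1. End of heparin, place by place.**

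| Place | Heparin ends at | Names the switch to Lovenox? |
|---|---|---|
| 9.3.2 item 3 | 48-hour CT scan | No |
| 7.1.1 item 2 | End of r-tPA infusion | No |
| 7.1.4 | End of r-tPA infusion | No |
| 7.1.5 | End of r-tPA infusion | No |
| 10.1 items 5-6 | End of r-tPA infusion | Yes |
| Appendix 21.1 footnote 3 | End of r-tPA infusion | Yes |
| Synopsis | End of r-tPA infusion, by implication | Yes |

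Five places contradict 9.3.2 item 3 explicitly and the synopsis does so by implication. Two of the five also name the switch. Section 7.1.5 has almost the same sentence as 9.3.2 with the other end point, so the intended regimen is not in doubt.

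**Step 2. Can the texts be reconciled?** After r-tPA, heparinized saline runs through the catheter at a keep-open rate (synopsis; 10.1 item 8). That is a patency flush through the catheter. Item 3 is an infusion through the sheath with an aPTT range and a therapeutic aim. The flush does not explain the clause.

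**Step 3. Overlap on a literal reading, in hours after r-tPA ends.**

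- First Lovenox dose: 45 ± 15 min, so 0.5 to 1.0 h.
- CTA (10.4.1): 48 ± 6 h, so 42 to 54 h.
- Overlap = CTA time − first Lovenox dose.
- Shortest: 42 − 1.0 = 41 h. Nominal: 48 − 0.75 = 47.25 h. Longest: 54 − 0.5 = 53.5 h.
- On the nominal schedule, four Lovenox doses fall in the overlap, at 0.75, 12.75, 24.75 and 36.75 h.

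**Step 4. Position in the 72-hour window.**

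- Infusion time (Table 2): unilateral 750/95 = 7.89 h; bilateral 500/65 = 7.69 h.
- CTA after infusion start: 7.69 + 42 = 49.7 h to 7.89 + 54 = 61.9 h.
- Margin to 72 h: 72 − 61.9 = 10.1 h. This assumes an uninterrupted infusion. Pauses for the pulse sprays would have to add more than 10 h to change the result.

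**Step 5. After the correction.** Heparin stops at 7.7 to 7.9 h and Lovenox starts 0.5 to 1.0 h later, so the overlap is 0 h.

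**Separate minor item.** Appendix 21.1 footnote 2 suggests an aPTT of 40-60 s during r-tPA, but 60-80 s at the check 4 ± 1 h after heparin restarts. That check falls wholly within the r-tPA infusion if heparin restarts within 7.69 − 5 = 2.7 h of infusion start, so the two ranges then apply at the same time.

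**The case against.** The strongest reply is that the protocol already controls the moment of danger. Section 10.1 item 6 puts both actions in one ICU instruction: heparin off, then Lovenox. It is later and more specific than 9.3.2, and four other places agree with it on when heparin ends. Double anticoagulation would require staff to follow the cath lab clause over an explicit stop order. This stands, and it is why the point is graded moderate. It does not make the clause correct, because the drip is started under 9.3.2 and nothing there points to 10.1.

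Four stronger readings are tempting and are not supported:

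- A reader might infer that patients will receive two days of combined anticoagulation. The 41 to 53.5 h figure is what the clause orders, not a forecast. The route is the sheath, and 10.5.3 wants the sheath out as soon as possible after the catheter.
- Conversely, a reader might infer a firm upper limit from the catheter removal window in 10.2. Section 10.5.3 leaves sheath timing to the investigator and the patient's coagulation status, so the protocol sets no such limit.
- A reader might take the −4 h tolerance in 10.6.1 to mean that bleeding is first assessed at 68 h. That tolerance applies to the end of assessment; adverse events are also collected during the procedure and through 24 and 48 h.
- A reader might count all five places as stating the Lovenox switch. Only 10.1 item 6 and Appendix 21.1 footnote 3 do. In addition, 7.1.1 item 2 is a laboratory item framed around standard of care, and 7.1.5 covers only patients given Lovenox beforehand.

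**Conclusion.** Section 9.3.2 item 3 is wrong as written. It is an internal inconsistency of moderate severity, and no design decision is in question. The conflict lies between current operative sections and does not rest on the version history.

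The literal size is 41 to 53.5 h of heparin with Lovenox (47.25 h nominal), all within the 72-hour primary bleeding window, assuming no long interruption of the r-tPA infusion. The actual overlap lies between zero, where 10.1 item 6 is followed, and that literal figure. It would be shortened if heparin stops at sheath removal. The documents do not allow the effect on bleeding to be computed. The aPTT mismatch in Appendix 21.1 footnote 2 is minor, since those ranges are only suggested, and it adds nothing to the grading.

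**What to change.** In 9.3.2 item 3, change the end point of the heparin infusion from the 48-hour CT scan to completion of the r-tPA infusion. Add a cross-reference to 10.1 item 6 for the switch to Lovenox, and notify the sites. As a separate minor edit, bring the suggested aPTT at the 4-hour check in Appendix 21.1 footnote 2 into line with the 40-60 s suggested during r-tPA.

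The cost is one clause, one cross-reference, one footnote and a site notice in a single amendment. No patients, procedures or data collection are added.
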